## **10. Supporting Documentation and Operational Considerations**

### **10.1 Regulatory, Ethical, and Study Oversight Considerations**

#### **10.1.1 Informed Consent Process**

### **10.1.1.1 Consent/Assent and Other Informational Documents Provided to Participants**

Consent forms describing in detail the study intervention, study procedures, and risks are given to the participant and written documentation of informed consent is required prior to starting intervention/administering study intervention. The following consent materials are submitted with this protocol:

- Appendix 1 (Subject Record at Screening Participant questionnaire – General information & PQi and GQi Evaluation Questionnaire )
- Appendix 2 (Physical Examination for screening visit)
- Appendix 3 (Subject Record at Follow-up Participant questionnaire – General information)
- Appendix 4 (Subject Record at Follow-up Participant questionnaire – PQi and GQi Evaluation Questionnaire)
- Appendix 5 (Subject Record at Follow-up Global Health assessment)
- Appendix 6 (Subject Record at Follow-up Emotional and Behavioral Dyscontrol Assessment-Short Form)
- Appendix 7 (Subject Record at Follow-up Emotional Impact assessment– Short Form)
- Appendix 8 (Subject Record at Follow-up Information and Consent Form)

### **10.1.1.2 Consent Procedures and Documentation**

Informed consent is a process that is initiated prior to the individual's agreeing to participate in the study and continues throughout the individual's study participation. Consent forms will be Institutional Review Board (IRB)-approved and the participant will be asked to read and review the document. The investigator will explain the research study to the participant and answer any questions that may arise. A verbal explanation will be provided in terms suited to the participant's comprehension of the purposes, procedures, and potential risks of the study and of their rights as research participants. Participants will have the opportunity to carefully review the written consent form and ask questions prior to signing. The participants should have the opportunity to discuss the study with their family or surrogates or think about it prior to agreeing to participate. The participant will sign the informed consent document prior to any procedures being done specifically for the study. Participants must be informed that participation is voluntary and that they may withdraw from the study at any time, without prejudice. A copy of the informed consent document will be given to the participants for their records. The informed consent process will be conducted and documented in the source document (including the date), and the form signed, before the participant undergoes any study-specific procedures. The rights and welfare of the participants will be protected by emphasizing to them that the quality of their medical care will not be adversely affected if they decline to participate in this study.

### **10.1.2 Study Discontinuation and Closure**

This study may be temporarily suspended or prematurely terminated if there is sufficient reasonable cause. Written notification, documenting the reason for study suspension or termination, will be provided by the suspending or terminating party to study participants, Principal Investigator, and sponsor. If the study is prematurely terminated or suspended, the Principal Investigator (PI) will promptly inform study participants, the Institutional Review Board (IRB), and sponsor and will provide the reason(s) for the termination or suspension. Study participants will be contacted, as applicable, and be informed of changes to study visit schedule.

Circumstances that may warrant termination or suspension include, but are not limited to:

- Determination of unexpected, significant, or unacceptable risk to participants
- Demonstration of efficacy that would warrant stopping
- Insufficient compliance to protocol requirements
- Data that are not sufficiently complete and/or evaluable
- Determination that the primary endpoint has been met
- Determination of futility

Study may resume once concerns about safety, protocol compliance, and data quality are addressed, and satisfy the sponsor, IRB

### **10.1.3 Confidentiality and Privacy**

Participant confidentiality and privacy is strictly held in trust by the participating investigators, their staff, and the sponsor(s) and their interventions. This confidentiality is extended to cover testing of biological samples and genetic tests in addition to the clinical information relating to participants. Therefore, the study protocol, documentation, data, and all other information generated will be held in strict confidence. No information concerning the study or the data will be released to any unauthorized third party without prior written approval of the sponsor.

All research activities will be conducted in as private a setting as possible.

The study monitor, other authorized representatives of the sponsor, representatives of the Institutional Review Board (IRB) may inspect all documents and records required to be maintained by the investigator, including but not limited to, medical records (office, clinic, or hospital) and pharmacy records for the participants in this study. The clinical study site will permit access to such records.

The study participant's contact information will be securely stored at clinical site for internal use during the study. At the end of the study, all records will continue to be kept in a secure location for as long a period as dictated by the reviewing IRB, sponsor requirements.

Study participant research data, which is for purposes of statistical analysis and scientific reporting, will be transmitted to and stored at the **ShareFile database** (an HIPPA compatible data sharing platform). This will not include the participant's contact or identifying information. Rather, individual participants and their research data will be identified by a unique study identification number. The study data entry and study management systems used by clinical sites and by statistician will be secured and password protected. At the end of the study, all study databases will be de-identified and archived at the **ShareFile database**.

#### **10.1.4 Future Use of Stored Data**

After completion of the study, documents and files generated from this trial will be shipped to and stored at the sponsor site (USANA). Digital, de-identified data collected for this study will be analyzed and stored at the **ShareFile Database**. After the study is completed, archived digital data will be transmitted to and stored at the **USANA Data Management Database**, for use by other researchers including those outside of the study. Permission to transmit data to the **USANA Data Management Database** will be included in the informed consent.

When the study is completed, access to study data and/or samples will be provided through the **USANA R&D**.

#### **10.1.5 Quality Assurance and Quality Control**

##### **10.1.5.1 Regulatory Compliance**

The investigators must agree to comply with the sponsor and regulatory requirements in terms of auditing of the study. This includes access to the source documents for source data verification at any time by the sponsor. In addition, the sponsor and investigators (as appropriate) will permit trial-related monitoring, audits, IRB/IEC review, and regulatory inspections and will allow direct access to source data and documents for these purposes. An initiation meeting will be conducted by the sponsor. At this meeting, the protocol and logistical aspects of the study will be reviewed by the Sponsor with the investigators and all study staff.

##### **10.1.5.2 Data Monitoring**

Source documents will be reviewed during an audit performed by the sponsor at four to six weeks from the beginning of the study (i.e., as indicated by enrollment of the first participant) and at the conclusion of the study following the release of the final participant. This will be done to ensure that all data is being properly gathered and recorded in accordance with the manner specified in the protocol. The participant files will be reviewed to confirm that:

- Informed consent was obtained and documented;
- Enrolled participants fulfilled all inclusion criteria and did not meet any exclusion criteria;
- AE/SAE reporting has been performed as applicable;
- Study visits have been conducted as per protocol and information has been recorded in the appropriate place in the source document;
- The study product is being stored correctly and an accurate record of its dispensation to the study participants is being maintained (accountability).

Incorrect, inappropriate, or illegible entries in the participant files will be returned to the investigator for correction. No data disclosing the identity of participants will leave the study center. The Investigator and any designees will maintain confidentiality of all participant records.

## **10.1.6 Data Handling and Record Keeping**

### **10.1.6.1 Data Collection and Management Responsibilities**

All data collection and record storage will be done in compliance with ICH GCP Guidelines and applicable local regulatory guidelines. Data required for analysis will be acquired from source documentation (including laboratory reports) and entered into a Microsoft Excel and other statistical software (R) for this study. All data points entered into the study database are source data verified.

### **10.1.6.2 Study Records Retention**

High safety standards for the transfer and storage of study data are guaranteed by the use of technologies such as password protection, firewalls and periodic backup to protect stored data. Writing access to the system will be limited to authorized personnel. All data is archived for a period not less than 20 years from the date of completion of the study.

**Table 1. Calculation of Standardized Protective Qi Deficiency (PQD)**

Category	Parameter	Weight
Cold History	TCM Inquiry (Cold frequency)	25%
Symptoms of PQD	TCM Inquiry (Spontaneous sweating)	16.7%
	TCM Inquiry (Aversion to wind & cold)	16.7%
Sign of PQD	TCM Inspection (Tongue)	8.3%
	TCM Auscultation (Low voice & apathy)	6.7%
	TCM Palpation (Overall Pulse)	10%
	TCM Palpation (Cun Pulse)	16.7%

The PQD were obtained from the standardized protocol shown in Table 2, and the weighting coefficients were based on TCM investigators' clinical experience. The range of the PQD index is 1-5, with the higher value indicating more severe PQD.

**Table 2: Standardized criteria for PQi severity score assessment**

Candidate Parameter		Method of measurement and scores	
Cold Frequency	TCM Inquiry (Cold frequency)	No cold in the past 2 months	0
		Once in the past 2 months	1
		Twice in the past 2 months	2
		3 times or more in the past 2 months	3
Symptoms of PQD	TCM Inquiry (Spontaneous sweating)	No spontaneous sweating, sweat only with intense physical activities	0
		Sweat with routine physical activities	1
		Sweat heavily with routine physical activities	2
		Sweat with slight physical activities like walking	3
		Sweat spontaneously	4
	TCM Inquiry (Aversion to wind & cold)	No aversion to wind or cold	0
		Aversion to wind	1
		Aversion to cold, but relieved by adding light clothing	2
		Aversion to both cold (but relieved by light clothing) and wind, or susceptible to cold when exposed to wind or cold	3
		Aversion to cold (only relieved by thick clothing that covers whole body); or very easily catch a cold when exposed to wind or cold	4
Sign of PQD	TCM Auscultation (Low voice & apathy)	The participant's voice is loud & clear at a distance of 2m from the investigator	0
		The participant can be heard & understood at 2m from the investigator, but the voice is recognizably weak.	1
		The participant's voice is clearly low at 2m from the investigator & needs much attention to understand.	2
		The participant can be heard from 2m but need repeated clarification.	3
		The participant cannot be heard with a clear understanding at a distance of 2m.	4
	TCM Inspection (Tongue)	The tongue looks light red with thin white coating and is of proper size.	0
		The tongue looks pale in color with white coating; however, the tongue is of proper size & has no tooth mark on the sides.	1
		The tongue looks pale with white coating. This size is slightly larger than normal. Tooth-marks are visible but are limited to part(s) of the tip and sides of the tongue.	2
		The tongue looks pale with white coating. This size is significantly larger than normal. Tooth-marks are visible along the full length of the tip and sides of the tongue.	3
	TCM Palpation (Overall Pulse  )	Normal pulse	0
		Deficient Pulse is detectable but not apparent	1
		Apparent Deficient Pulse	2
	TCM Palpation (Cun Puls  )	Normal pulse	0
		The pulse shows characteristics of Floating or Deficient Pulse, but not both.	1
		Floating pulse is present, Deficient Pulse is detectable but not apparent.	2
		Floating pulse is present, Deficient Pulse is apparent.	3

1. Overall pulse indicates the overall impression of pulse at the three locations: Cun, Guan, & Chi.

**Table 3. Calculation of Standardized Generic Qi Deficiency (GQD)**

Final Score	Subscore D	Subscore C	Subscore B	Subscore A	
GQD Score Weighted sum of Subscore Ds Symptom Score Wt: 40% Sing Score Wt: 60%	Symptom Score Select the highest one among Subscore Cs of Part I-VI	Part I : Symptoms of PQD Score Weighted sum of Subscore Bs Part Ia Wt: 47% Part Ib Wt: 53%	Part I a: Score of cold history	TCM Inquiry (Cold frequency)	
			Part I b: Score of other PQD symptoms Weighted sum of Subscore As. Ib 1 Wt. 50% Ib 2 Wt. 50%	Ib1: TCM Inquiry (Spontaneous sweating)	
		Part II: Symptoms of Systemic Qi Deficiency Score Average subscore As of IIa-d	Ib2	TCM Inquiry (Aversion to wind & cold)	
			IIa:	TCM Inquiry (Limb weakness)	
			IIb:	TCM Inquiry (Lack of energy)	
			IIc:	TCM Inquiry (Low spirit)	
			IId:	TCM Inquiry (Unwilling to talk)	
			IIIa:	TCM Inquiry (Shortness of Breath )	
			IIIb:	TCM Inquiry (Cough)	
			IIIc:	TCM Inquiry (Thin sputum)	
			IIId:	TCM Inquiry (Timidity)	
			Part IV: Symptoms of Spleen Qi Deficiency Score Average subscore As of IVa-c	IVa:	TCM Inquiry (Poor appetite)
				IVb:	TCM Inquiry (Loose stools)
				IVc:	TCM Inquiry (Abdominal discomfort feeling after eating)
		Part V: Symptoms of Heart Qi Deficiency Score Average subscore As of Va-b	Va:	TCM Inquiry (Palpitations)	
			Vb:	TCM Inquiry (Depressed)	
		Part VI: Symptoms of Kidney Qi Deficiency Score Average subscore As of VIa-c	VIa:	TCM Inquiry (Urination)	
			VIb:	TCM Inquiry (Soreness of lower back)	
			VIc:	TCM Inquiry (Cold limbs especially legs)	
		Sign of GQD Weighted sum of Subscore As Part I-IV Part I Wt: 24%, Part II Wt: 40%, Part III Wt: 20%, Part IV Wt: 16%	Part I:	TCM Auscultation ( Low voice & apathy )	
			Part II:	TCM Inspection ( Tongue )	
			Part III:	TCM Palpation (Overall Pulse  )	
			Part IV:	TCM Palpation (Cun Puls  )	

The GQD severity score were obtained from the standardized protocol shown in Table 4, and the weighting coefficients were based on TCM investigators’ clinical experience. The range of the GQD index is 1-5, with the higher value indicating more severe GQD.

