# Attachment I: Insufficiency of Protective Qi (IPQ) Index

Final score	Subscore C	Subscore B	Subscore A		
IPQ index, Weighted sum of Subscore Cs. Part I Wt.: 25%, Part II Wt.: 33.3%, Part III Wt.: 41.7%	Part I: Score of Cold History, Weighted sum of Subscore Bs. Ia1 Wt. 66.7%, Ia2 Wt. 33.3%	Part Ia1: Cold* frequency (in the past 2 month & recovery (total time if $\geq$ once), select from Subscore As one that applies	no Cold* at all	1	
			Once & recovered within 3day	2	
			Once & recovered within 1wk	3	
			Once & recovered within 2wk	4	
			Once & recovered $\geq$ 2 wk	5	
			Twice & recovered within 3day	6	
			Twice & recovered within 1wk	7	
			Twice & recovered within 2wk	8	
			Twice & recovered $\geq$ 2 wk	9	
			3 time or more	10	
		Part Ia2: Cold* related symptoms; Sum of Subscore As + 1	Sneezing	1 if yes	
			Coughing	1 if yes	
			Sweating	1 if yes	
			Nasal discharge or congestion	1 if yes	
			Itching or painful throat	1 if yes	
	Headache		1 if yes		
	Aversion to wind and cold		1 if yes		
	General pain and malaise		1 if yes		
	Part II, Score of Other IPQ symptoms, Weighted sum of Subscore Bs. Ib1 Wt. 50%, Ib2 Wt. 50%	Part IIa: Spontaneous sweating, Select from Subscore As one that applies	High fever ( $\geq$ 39.10C)	1 if yes	
			Don't readily sweat, or sweat only with intense physical activities	1	
			sweat with some slight physical activities like walking	2	
			Sweat spontaneously	3	
			Sweat heavily and instantly with physical activities	4	
		Part IIb: Aversion to wind or cold, Select from Subscore As one that applies	Sweat even without any physical activities	5	
			No aversion to wind or cold	1	
			Aversion to wind	2	
			Aversion to cold, but relieved by adding clothing	3	
			Aversion to both cold (but relieved by clothing) and wind, or susceptible to cold* when exposed to wind or cold weather	4	
			Aversion to cold (only relieved by clothing that cover whole body), very readily catch a cold* when exposed to wind or cold weather	5	
			Part III: Sign Score, Weighted sum of Subscore As. of Part I- IV; Part I Wt. 24%, Part II Wt. 40%, Part III, 20%, Part IV, 16%		Part I: weak or powerless pulse
Part II: chun-pulse superficial or weak					Scale 1-5
Part III: corpulent tongue or with white fur					Scale 1-5
Part IV: low voice					Scale 1-5

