		Part III: Lung* Qi Insufficiency Score, average Subscore As of IIIa-d	IIIa: often feel shortness of breath	Scale 1-5		
			IIIb: often have a cough	Scale 1-5		
			IIIc: often have thin sputum	Scale 1-5		
			IIId: often feel timidity	Scale 1-5		
		Part IV: Spleen* Qi Insufficiency Score, average Subscore As of IVa-c	IVa: often have poor appetite	Scale 1-5		
			IVb: have loose stools	Scale 1-5		
			IVc: often have abdominal discomfort feeling after eating	Scale 1-5		
Part V: Heart* Qi Insufficiency Score, average Subscore As of Va-c	Va: often feel palpitations	Scale 1-5				
	Vb: often feel depressed	Scale 1-5				
	Va: frequent urination	Scale 1-5				
Part VI: Kidney* Qi Insufficiency Score, average Subscore As of VIa-c	VIb: often feel soreness of lower back	Scale 1-5				
	VIc: have cold limbs especially legs	Scale 1-5				
	Part I: weak or powerless pulse	Scale 1-5				
	Part II: chun-pulse superficial or weak	Scale 1-5				
Sign Score, Weighted sum of Subscore As. Part I- IV; Part I Wt. 24%, Part II Wt. 40%, Part III, 20%, Part IV, 16%	Part III: corpulent tongue or with white fur	Scale 1-5				
	Part IV: low voice	Scale 1-5

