**Table 4: Standardized criteria for GQi severity score assessment**

Candidate Parameter		Method of measurement and scores	
Symptoms of PQD	Ia: TCM Inquiry (Cold frequency)	No cold in the past 2 months	0
		Once in the past 2 months	1
		Twice in the past 2 months	2
		3 times or more in the past 2 months	3
	Ib1: TCM Inquiry (Spontaneous sweating)	No spontaneous sweating, sweat only with intense physical activities	0
		Sweat with routine physical activities	1
		Sweat heavily with routine physical activities	2
		Sweat with slight physical activities like walking	3
		Sweat spontaneously	4
	Ib2: TCM Inquiry (Aversion to wind & cold)	No aversion to wind or cold	0
		Aversion to wind	1
		Aversion to cold, but relieved by adding light clothing	2
Aversion to both cold (but relieved by light clothing) and wind, or susceptible to cold when exposed to wind or cold		3	
Aversion to cold (only relieved by thick clothing that covers whole body); or very easily catch a cold when exposed to wind or cold		4	
Symptoms of Systemic Qi Deficiency	IIa: TCM Inquiry (Limb weakness)	1-5 scale, with 5 indicating the most symptomatic	
	IIb: TCM Inquiry (Lack of energy)		
	IIc: TCM Inquiry (Low spirit)		
	IId: TCM Inquiry (Unwilling to talk)		
Symptoms of Lung Qi Deficiency	IIIa: TCM Inquiry (Shortness of Breath)	1-5 scale, with 5 indicating the most symptomatic	
	IIIb: TCM Inquiry (Cough)		
	IIIc: TCM Inquiry (Thin sputum)		
	IIId: TCM Inquiry (Timidity)		
Symptoms of Spleen Qi Deficiency	Iva: TCM Inquiry (Poor appetite)	1-5 scale, with 5 indicating the most symptomatic	
	IVb: TCM Inquiry (Loose stools)		
	IVc: TCM Inquiry (Abdominal discomfort feeling after eating)		
Symptoms of Heart Qi Deficiency	Va: TCM Inquiry (Palpitations)	1-5 scale, with 5 indicating the most symptomatic	
	Vb: TCM Inquiry (Depressed)		
Symptoms of Kidney Qi Deficiency	VIa: TCM Inquiry (Urination)	1-5 scale, with 5 indicating the most symptomatic	
	VIb: TCM Inquiry (Soreness of lower back)	1-5 scale, with 5 indicating the most symptomatic	
	VIc: TCM Inquiry (Cold limbs especially legs)	1-5 scale, with 5 indicating the most symptomatic	
Sign of GQD	Part I: TCM Auscultation (Low voice & apathy)	The participant's voice is loud & clear at a distance of 2m from the investigator	0
		The participant can be heard & understood at 2m from the investigator, but the voice is recognizably weak.	1
		The participant's voice is clearly low at 2m from the investigator & needs much attention to understand.	2

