		The participant can be heard from 2m but need repeated clarification.	3
		The participant cannot be heard with a clear understanding at a distance of 2m.	4
	Part II: TCM Inspection (Tongue)	The tongue looks light red with thin white coating and is of proper size.	0
		The tongue looks pale in color with white coating; however, the tongue is of proper size & has no tooth mark on the sides.	1
		The tongue looks pale with white coating. This size is slightly larger than normal. Tooth-marks are visible but are limited to part(s) of the tip and sides of the tongue.	2
		The tongue looks pale with white coating. This size is significantly larger than normal. Tooth-marks are visible along the full length of the tip and sides of the tongue.	3
	Part III: TCM Palpation (Overall Pulse)	Normal pulse	0
		Deficient Pulse is detectable but not apparent	1
		Apparent Deficient Pulse	2
	Part IV: TCM Palpation (Cun Puls)	Normal pulse	0
The pulse shows characteristics of Floating or Deficient Pulse, but not both.		1	
Floating pulse is present, Deficient Pulse is detectable but not apparent.		2	
Floating pulse is present, Deficient Pulse is apparent.		3	

Overall pulse indicates the overall impression of pulse at the three locations: Cun, Guan, & Chi.

# Appendix 1

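### Tables 3 and 4 give a GQD score running from 0.40 to 3.82, not the stated 1-5; the symptom maximum compares unequal scales, and the sign weights conflict with Table 1 and Attachments I-II

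*Combined protocol and SAP*

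**What the plan says.** Section 9.4.2 of the combined protocol and SAP sends the reader to Table 4 for the item codes and Table 3 for the weights, says the score lies between 1 and 5, and makes change from baseline the outcome. The note under Table 3 repeats the range: "The range of the GQD index is 1-5, with the higher value indicating more severe GQD". It names Table 4 as the source of the scores and states no rescaling.

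Table 3 builds the index as 40% symptom score plus 60% sign score. For the symptom score the rule is "Select the highest one among Subscore Cs of Part I-VI". Part I holds the protective-Qi symptoms, and Parts II-VI hold the systemic, lung, spleen, heart and kidney symptoms. Table 4 codes the Part I items from 0, but each item in Parts II-VI is on a "1-5 scale, with 5 indicating the most symptomatic".

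For the signs, Table 3 gives "Part I Wt: 24%, Part II Wt: 40%, Part III Wt: 20%, Part IV Wt: 16" (per cent) and numbers them voice, tongue, overall pulse, Cun pulse. Table 4 uses the same numbering and ends with "Part IV: TCM Palpation (Cun Puls", so the order is not an accident of text extraction.

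Attachments I and II, in the separate Protocol document, carry the same sequence of weights, "Part I Wt. 24%, Part II Wt. 40%, Part III, 20%, Part IV, 16" (per cent), on a different order of signs: weak pulse, Cun pulse, tongue, low voice. The 40% entry in Attachment II is "Part II: chun-pulse superficial or weak". Table 1, for the protective-Qi score, gives its largest sign weight (16.7%) to "TCM Palpation (Cun Pulse)".

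**The concern.** Tables 3 and 4 are the operative scoring rule for GQD, and strengthening general Qi is the named secondary objective. A stated 1-5 range that the item codes cannot produce means that either the codes or the range is wrong. Taking a maximum across domains is sensible only if the domains share a scale. Here the domain closest to the product's presumed action is the one with the lower floor and the lower ceiling. The same four percentages also sit on different signs in different tables, so an analyst following Table 3 and one following the Table 1 or Attachment assignment would obtain different changes from baseline for the same participant.

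**Working it through.** **Inputs (Table 3 weights, Table 4 codes).** Index = 0.40 × symptom score + 0.60 × sign score. Part I = 0.47 × cold + 0.53 × (0.5 × sweating + 0.5 × aversion), with cold 0-3, sweating 0-4 and aversion 0-4. Parts II-VI are averages of 1-5 items. Signs: voice 0-4, tongue 0-3, overall pulse 0-2, Cun pulse 0-3.

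**1. The stated 1-5 range.** The symptom maximum runs from 1 (the floor of Parts II-VI) to 5. The sign score runs from 0 to 0.24×4 + 0.40×3 + 0.20×2 + 0.16×3 = 3.04.

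- Minimum: 0.40×1 + 0.60×0 = 0.40
- Maximum: 0.40×5 + 0.60×3.04 = 3.824

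The plan's 1-5 is not reproduced. Three variants were tried:

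| Variant | Minimum | Maximum |
|---|---|---|
| Add 1 to every zero-based item | 0.40×1 + 0.60×1 = 1.00 | 0.40×5 + 0.60×4.04 = 4.42 |
| Keep Table 4 codes, use Table 1/Attachment sign weights | 0.40 | 0.40×5 + 0.60×(0.16×4 + 0.20×3 + 0.24×2 + 0.40×3) = 2 + 0.60×2.92 = 3.75 |
| Attachment II item codes | 1.00 | 5.00 |

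In the first variant Part I reaches 3.53 + 1 = 4.53, so the symptom maximum is still 5. In the third, signs run 1-5 and Part I runs from 0.47×(0.667×1 + 0.333×0.5) + 0.53×1 = 0.92 to 5; the other domains supply the floor of 1. Only this variant gives 1-5, and it is not the coding that Table 3 cites.

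**2. The symptom maximum.** Part I runs from 0 to 0.47×3 + 0.53×4 = 3.53, against 1-5 for Parts II-VI. Of the 4×5×5 = 100 Part I code combinations, 17 give a value of at most 1. In those, Part I cannot lift the symptom score above its floor. The count runs over codes and is not a patient frequency.

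This affects change scores. Suppose cold, sweating and aversion are each coded 1, and all Part II-VI items are at 1. Part I = 0.47 + 0.53 = 1.00, so the symptom score is 1. If all three items fall to 0, the symptom score is still 1 and the recorded change is zero. With Part I linearly rescaled to 1-5, it would fall from 1 + 4×1.00/3.53 = 2.13 to 1, and GQD would fall by 0.40×1.13 = 0.45.

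**3. The sign weights.** Table 1's sign weights as shares of their 41.7% block: overall pulse 10/41.7 = 24.0%, Cun pulse 16.7/41.7 = 40.0%, tongue 8.3/41.7 = 19.9%, voice 6.7/41.7 = 16.1%. These match Attachments I-II.

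| Sign | Table 3 | Table 1 and Attachments I-II | GQD per step, Table 3 | GQD per step, other |
|---|---|---|---|---|
| Voice | 24% | 16% | 0.60×0.24 = 0.144 | 0.60×0.16 = 0.096 |
| Tongue | 40% | 20% | 0.60×0.40 = 0.24 | 0.60×0.20 = 0.12 |
| Overall pulse | 20% | 24% | 0.60×0.20 = 0.12 | 0.60×0.24 = 0.144 |
| Cun pulse | 16% | 40% | 0.60×0.16 = 0.096 | 0.60×0.40 = 0.24 |

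The two pulse signs carry a nominal 36% under Table 3 and 64% otherwise. As a share of the maximum sign score under Table 4 codes, they carry (0.20×2 + 0.16×3)/3.04 = 0.88/3.04 = 29%, against (0.24×2 + 0.40×3)/2.92 = 1.68/2.92 = 58%.

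**The case against.** The strongest reply is that GQD and PQD are different constructs and may be weighted differently on purpose. Nothing in the documents requires equal sign weights, and the note under Table 3 attributes the weights to the investigators' clinical experience. Attachments I-II form a separate document, undated in the text available, with different items (a ten-level cold history and a count of cold symptoms), so they cannot settle current intent alone. This stands. A reader might infer that the transposition in Table 3 is proven. It is likely, because the same four numbers recur in the same Part I-IV sequence, but it remains an inference. The range and the maximum need no such inference.

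Second, a constant offset cancels in change from baseline, and the two sign weightings are related: over all 5×4×3×4 = 240 sign patterns, equally weighted (an assumption), the two sign scores correlate at 0.81. Both are fair, but neither the per-step weights nor the maximum rule is an offset.

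Third, GQD is a secondary endpoint, a traditional GQD diagnosis stands beside it, and both blinded arms are scored alike. That stands, and it limits the severity.

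A reader might also infer from the forms that some baseline GQD values cannot be recomputed, or that Appendix 4's last sweating option has no Table 4 code. The documents do not support either. Section 9.4.2 applies Tables 3 and 4 at baseline, and the visit schedule cited as Sections 1.2 and 1.3 is not in the text available. Sweating without activity can be read as Table 4's top category.

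**Conclusion.** The concern holds, and should be fixed, on three counts. The printed GQD range is 0.40-3.82 against a stated 1-5. The symptom maximum compares a 0-3.53 domain with 1-5 domains, which under-selects the protective-Qi domain. The sign weights contradict Table 1 and Attachments I-II, which changes the effect of one Cun-pulse step by a factor of 2.5 (0.24/0.096) and that of one tongue step by a factor of 2 (0.24/0.12). The first two follow by arithmetic from Tables 3 and 4, given that no rescaling is stated. On the third, the documents show a conflict but not which assignment was meant.

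The effect is on the validity and sensitivity of a secondary endpoint. A reader might infer a biased comparison, but identical scoring in two blinded arms gives no ground for that. The sample size and the primary PQD score are outside this point. The conflicts between Appendices 1 and 4 and Tables 2 and 4 (sign scales of 1-10 or 1-5 against zero-based codes, three-month against two-month cold recall, order of the sweating options) also feed the primary score and belong in a separate point.

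**What to change.** - **Scale.** Put Part I and the sign items on the same 1-5 scale as Parts II-VI before taking the maximum and weighting. Use the 1-5 sign codes on Appendix 4 where those were collected, and otherwise a documented rescaling. If the codes are left as printed, correct the 1-5 range in Section 9.4.2 and under Table 3; the unequal maximum then remains and should be acknowledged.
- **Sign weights.** Reconcile Table 3 with Table 1 and Attachments I-II from source records, and state one assignment by sign name instead of Part number.
- **Process.** Record the decision in a dated note, blind to allocation. Version 4.0 is dated 18 February 2022 and Section 5.5 plans enrolment to end in March 2019, so a choice made now needs that protection.
- **Sensitivity.** Report the other weight assignment as a sensitivity analysis.

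The cost is low: a source-record check, a table correction, a short note, one re-scoring run and one sensitivity run.
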